9.4. Monitoring

The Sponsor will designate a Study Monitor(s) who will be responsible for monitoring this clinical trial. The Sponsor's Study Monitor(s) will monitor the study conduct, proper eCRF and source documentation completion and retention, and accurate study drug accountability. To this end, the Sponsor's Study Monitor(s) will visit the CRU(s) at suitable intervals (or may perform activities remotely as per the Monitoring Plan for this study) and be in frequent contact with the Investigator (or designee) and the Investigator's staff through verbal and written communication. It is essential that the Sponsor's Study Monitor(s) has access to all documents (related to the study and the individual participants) at any time these are requested. In turn, the Sponsor's Study Monitor(s) will adhere to all requirements for subject confidentiality as outlined in the ICF. The Investigator (or designee) and Investigator's staff will be expected to cooperate with the Sponsor's Study Monitor(s), to be available during a portion of the monitoring visit to answer questions, and to provide any missing information.

9.5. Institutional Review Board

In accordance with US Title 21 Code of Federal Regulations (CFR) 56, the protocol, advertisement, ICF, and other information provided to subjects will be reviewed and approved by the IRB. The Sponsor will supply relevant material for the Investigator (or designee) to submit to the IRB for the protocol's review and approval. Verification of the IRB unconditional approval of the protocol and the written ICF statement will be transmitted to the Investigator (or designee).

The IRB will be informed by the Investigator (or designee) of subsequent protocol amendments and of serious and unexpected AEs. Approval for protocol amendments will be transmitted in writing to the Investigator (or designee). If requested, the Investigator (or designee) will permit audits by the IRB and regulatory inspections by providing direct access to source data/documents.

The Investigator (or designee) will provide the IRB with progress reports at appropriate intervals (not to exceed 1 year) and a Study Progress Report following the completion, termination, or discontinuation of the Investigator's (or designee's) participation in the study.

9.6. Informed Consent

Written informed consent for the study will be obtained from all subjects before protocol-specific procedures are carried out. The ICF will be approved (along with the protocol) by the IRB and will be acceptable to the Sponsor.

The Investigator (or designee) will explain the nature of the study and the action of the test product. The subjects will be informed that participation is voluntary and that they can withdraw from the study at any time. In accordance with 21 CFR 50, the informed consent process shall be documented by the use of a written ICF approved by the IRB and signed by the subject prior to protocol-specific procedures being performed.

The subject will sign 2 copies of the ICF. One copy will be given to the subject, and the other will be maintained with the subject's records.

9.7. Records

The results from data collected at Screening and during the study will be recorded in the subject's eCRF. To maintain confidentiality, the subjects will be identified only by numbers.

The completed eCRFs will be transferred to the Sponsor (or designee). Copies of each eCRF will be retained by the Investigator (or designee). All source documents, records, and reports will be retained by the CRU in accordance with 21 CFR 312.62(c).

All primary data, or copies thereof (eg, laboratory records, eCRFs, data sheets, correspondence, photographs, and computer records), which are a result of the original observations and activities of the study and are necessary for the reconstruction and evaluation of any study report, will be retained in the CRU archives.

9.8. Reference to Declaration of Helsinki/Basic Principles

The study procedures outlined in this protocol will be conducted in accordance with the US CFR governing Protection of Human Subjects (21 CFR 50), Financial Disclosure by Clinical Investigators (21 CFR 54), IRBs (21 CFR 56), and Investigational New Drug Application (21 CFR 312), as appropriate. As such, these sections of US Title 21 CFR, along with the applicable International Council for Harmonisation Guidelines, are commonly known as Good Clinical Practices, which are consistent with the Declaration of Helsinki.

9.9. Financing and Insurance

Financing and insurance will be addressed in a separate agreement.

11. APPENDICES

Appendix 1: Adverse Event Reporting

Adverse Events

Definition of Adverse Events

An adverse event (AE; or adverse experience) is defined as any untoward medical occurrence experienced by a patient or healthy adult subject, whether or not considered drug-related by the Investigator (or designee). A treatment-emergent AE is an AE that starts on or after the first administration of study drug.

The following are all AEs:

- unfavorable changes in general condition
- subjective or objective signs/symptoms
- concomitant diseases or accidents
- clinically significant adverse changes in laboratory parameters observed in a subject during a clinical study.

Adverse events comprise all disturbances of general health status, subjective and objective disease symptoms (including laboratory abnormalities that are deemed clinically significant by the Investigator [or designee]), and accidents observed in the context of a clinical trial, irrespective of a possible causal relationship with the administration of the trial substance.

Categorization of Adverse Events

The severity of AEs will be categorized based on the National Cancer Institute Common Terminology Criteria for Adverse Events (CTCAE) Version 5.0 as follows:

- **Grade 1 Mild:** Asymptomatic or mild symptoms; clinical or diagnostic observations only; intervention not indicated
- **Grade 2 Moderate:** Minimal, local, or noninvasive intervention indicated; limiting age-appropriate instrumental Activities of Daily Living (ADL)*
- **Grade 3 Severe or medically significant but not immediately life-threatening:** Hospitalization or prolongation of hospitalization indicated; disabling; limiting self-care ADL**
- **Grade 4 Life-threatening consequences:** An event that puts the subject at immediate risk of death
- **Grade 5:** Death related to AE

Note: Not all grades are appropriate for all AEs. Therefore, some AEs are listed within the CTCAE with fewer than 5 options for grade selection. Grade 5 (death) is not appropriate for some AEs and therefore is not an option.

* Instrumental ADL refer to preparing meals, shopping for groceries, or clothes, using the telephone, managing money, etc.

**Self-care ADL refer to bathing, dressing and undressing, feeding self, using the toilet, taking medications, and not bedridden.

The Investigator (or designee) will make a determination of the relationship of the AE to the study drug using a 2-category system according to the following guidelines:

- **NOT RELATED** = The time course between the administration of investigational product and the occurrence or worsening of the AE rules out a causal relationship and another cause (eg, concomitant drugs, therapies, complications, comorbidities) is suspected.
- **RELATED** = The time course between administration of investigational product and the occurrence or worsening of the AE is consistent with a causal relationship and no other cause (eg, concomitant drugs, therapies, complications, comorbidities) can be identified.

An AE is associated with the use of the drug if there is a reasonable possibility that the experience may have been caused by the drug.

Pregnancy

As information is available, a pregnancy (including pregnancy in female partners of male subjects) diagnosed through End of Study or Early Termination (ET; if the subject discontinues from the study and does not complete a follow-up phone call) and for up to 90 days after study drug administration on Day 8 (or last administration of study drug if subject terminates from the study early) should be reported by the Investigator (or designee) via email to Labcorp Drug Development or the Sponsor's Clinical Safety Representative within 24 hours of being notified. Labcorp Drug Development or the Sponsor's Clinical Safety Representative will then forward the Pregnancy Form to the Investigator (or designee) for completion.

email: [contact]

A subject becoming pregnant while on study drug will immediately be withdrawn from the study and ET study procedures will be performed. The subject or partner should be followed by the Investigator (or designee) until completion of the pregnancy. If the pregnancy ends for any reason before the anticipated date, the Investigator (or designee) should notify Labcorp Drug Development or the Sponsor's Clinical Safety Representative. At the completion of the pregnancy, the Investigator (or designee) will document the outcome of the pregnancy. If the outcome of the pregnancy meets the criteria for immediate classification as a serious adverse event (SAE; ie, postpartum complication, spontaneous abortion, stillbirth, neonatal death, or congenital anomaly), the Investigator (or designee) should follow the procedures for reporting an SAE.

Male subjects will be instructed to notify the Investigator (or designee) immediately if they discover their sexual partner is pregnant. In this instance, the partner must provide written consent before pregnancy information can be collected. When a Clinical Research Unit (CRU) becomes aware that the female partner of a male subject is pregnant, they are to contact the Investigator (or designee) immediately (within 24 hours of the CRU staff becoming aware of the event) in addition to notifying Labcorp Drug Development or the Sponsor's Clinical Safety Representative via email.

All pregnancies should be recorded on the AE electronic case report form (eCRF; as appropriate), in addition to completion of the required pregnancy forms. If the Investigator (or designee) suspects that a pregnancy was the result of an interaction between the study treatment and the contraceptive method, in addition to the pregnancy the drug interaction should also be captured as a separate AE.

Definition of Serious Adverse Events

An SAE by the Food and Drug Administration (FDA) definition is any adverse drug experience occurring at any dose that results in any of the following outcomes:

- Death
- A life-threatening adverse drug experience (ie, one that places the subject, in the view of the Investigator [or designee], at immediate risk of death)
- Inpatient hospitalization or prolongation of existing hospitalization
- A persistent or significant disability/incapacity
- A congenital anomaly/birth defect
- An important medical event that may require medical or surgical intervention to prevent 1 of the above outcomes.

Important medical events that may not result in death, be life-threatening, or require hospitalization may be considered SAEs when, based on appropriate medical judgment, they may jeopardize the patient or subject and may require medical or surgical intervention to prevent 1 of the outcomes listed in this definition.

Unexpected Adverse Drug Reaction

An AE or suspected adverse drug reaction is considered ‘unexpected’ if the event is not listed in the Reference Safety Information section of the Investigator’s Brochure or if it is not listed at the specificity or severity that has been observed for an unapproved investigational medicinal product.

Reporting

The FDA-reportable AEs are AEs that are associated with the use of the drug and represent events that are assessed as serious, related, and unexpected. The FDA-reportable AEs will be reported by the CRU to the Sponsor and the responsible Institutional Review Board (IRB). Final determination of whether an event represents a suspected unexpected serious adverse reaction (SUSAR) will be the responsibility of the Sponsor.

Within 24 hours of when an AE that is potentially FDA-reportable is first recognized or reported, and within 24 hours of any SAE (regardless of whether the event is assessed as related or unrelated to study drug) being first recognized or reported, Labcorp Drug

Development or the Sponsor's Clinical Safety Representative will be notified by the Investigator (or designee) in writing using the following email address:

email: [contact]

To report the SAE, the completed report form should be sent by email to Labcorp Drug Development or the Sponsor's Clinical Safety Representative within 24 hours of awareness. Incoming reports are reviewed during normal business hours. Additional reporting instructions and the SAE Report Form are provided in the Study Manual.

The IRB will be notified of any FDA-reportable AE within the timeframe required by the IRB. The IRB Serious and Unexpected Adverse Experience Submission Form will be completed and submitted with the copy of the written confirmation or summary of the AE.

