8.4. Safety Analysis

All safety assessments, including AEs, SAEs, vital sign measurements, clinical laboratory results, physical examination results, concomitant medications, and 12-lead ECGs, will be tabulated and summarized where possible, using descriptive methodology, as needed, by timepoint. Unless otherwise specified, baseline value is defined as the last non-missing measurement before administration of study drug for each period (ie, Day 1 and Day 8). No formal statistical analyses are planned for the safety data. All safety data will be listed by subject.

Concomitant medications will be coded using the World Health Organization (WHO) Drug Dictionary (WHO Drug Global B3, September 2019). Adverse events will be coded using Medical Dictionary for Regulatory Activities Version 22.1 (or higher). The incidence of AEs will be presented by severity and by relationship to study drug as determined by the Investigator or designee ([Appendix 1](#) for AE reporting). All TEAEs will be summarized by system organ class and preferred term.

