8.6. Safety and Tolerability Assessments

8.6.1. Adverse Events

All AEs will be coded using the Medical Dictionary for Regulatory Activities (MedDRA) Version 24.1 (or higher if a new version is issued during the study; see the DMP for more details). All AEs will be assigned a severity grade using Common Terminology Criteria for Adverse Events (CTCAE) Version 5.0 (or higher if a new version is issued during the study; see the protocol for more details).

A treatment-emergent adverse event (TEAE) will be defined as an AE that starts during or after the first dose, or starts prior to the first dose and increases in severity after the first dose.

A treatment-related TEAE will be defined as a TEAE with a relationship of related to the study treatment, as determined by the investigator.

All AEs will be listed. In addition to the data recorded in the database, the listings will include derived onset time and duration. Onset time will be calculated from the time of the last associated dose for TEAEs only.

The frequency of subjects with TEAEs and the number of TEAEs will be summarized for the following categories:

- TEAEs (overall, serious, leading to discontinuation, and leading to death) by treatment
- TEAEs by severity and treatment
- Treatment-related TEAEs (overall, serious, leading to discontinuation, and leading to death) by treatment
- Treatment-related TEAEs by severity and treatment

The frequency of subjects will be summarized separately for TEAEs and treatment-related TEAEs by the following:

- System organ class, preferred term, and treatment
- Preferred term and treatment

For the AE data the following rules will apply:

- For the derivation of treatment-emergent status (applicable to all AEs): If the start date/time of an AE is incomplete or missing, an AE will be assumed to be a TEAE, unless the incomplete start date/time or the end date/time indicates an AE started prior to the first dose.
- For the derivation of treatment-related status (applicable to TEAEs only): If the study treatment relationship for a TEAE is missing, that TEAE will be counted under the 'missing' category.

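### An adverse event with drug-consistent timing and another identifiable cause fits neither causality category, and no passage says which causality standard governs

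*Protocol*

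**What the plan says.** Protocol Appendix 1 has the investigator judge the relationship of each AE to study drug "using a 2-category system according to the following guidelines". The two definitions follow:

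- NOT RELATED: the time course "rules out a causal relationship and another cause (eg, concomitant drugs, therapies, complications, comorbidities) is suspected".
- RELATED: the time course "is consistent with a causal relationship and no other cause (eg, concomitant drugs, therapies, complications, comorbidities) can be identified".

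The next sentence sets a test for another term. An AE is *associated* with use of the drug "if there is a reasonable possibility that the experience may have been caused by the drug". Under Reporting, the same appendix uses both terms: FDA-reportable AEs are "AEs that are associated with the use of the drug and represent events that are assessed as serious, related, and unexpected". It also has every SAE notified within 24 hours, "regardless of whether the event is assessed as related or unrelated to study drug", and leaves the final SUSAR determination to the sponsor.

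The label is then used in the analysis. Protocol 8.4 states: "The incidence of AEs will be presented by severity and by relationship to study drug as determined by the Investigator or designee". SAP 8.6.1 states: "A treatment-related TEAE will be defined as a TEAE with a relationship of related to the study treatment, as determined by the investigator". The SAP accepts the investigator's label as recorded and adds only a category for a missing relationship. Protocol 3.1 and 7.2.1 limit AE reporting after end of treatment (EOT) or early termination (ET) to events assessed as related; SAEs are reported throughout.

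**The concern.** A two-category scale should place every event in exactly one category. Here each definition joins a timing condition and a cause condition with *and*, so the two are not complements. The uncovered case that matters is an AE whose timing fits the drug but for which something else could also be responsible.

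That case is plausible in this study. Protocol 1.5 names discomfort from blood collection and other study procedures as a risk, and Appendix 3 allows up to 39 PK samples per subject. Protocol Table 2 lists petechiae (12) and headache (10) as the most frequent treatment-related events in earlier clinical pharmacology studies. These passages illustrate how a competing cause could arise; they do not show how often one would.

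With such an event, one investigator may decide that it fails RELATED and record NOT RELATED. Another may apply the reasonable-possibility sentence and record RELATED. Both can point to Appendix 1. Safety and tolerability is the secondary objective, so the label should mean the same thing whoever assigns it.

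**Working it through.** No figure in the plan needs reproducing. The check sets the definitions against each other.

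**Step 1. Cross timing with cause.** Timing is taken as either consistent with causality or ruling it out. Another cause is taken as either present or absent, so that *suspected* and *can be identified* are treated as the same thing.

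| Timing | Other cause | RELATED met? | NOT RELATED met? | Result |
|---|---|---|---|---|
| Consistent | Absent | Yes | No | RELATED |
| Consistent | Present | No, another cause exists | No, timing does not rule it out | Neither |
| Ruled out | Absent | No, timing fails | No, no other cause | Neither |
| Ruled out | Present | No | Yes | NOT RELATED |

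**Step 2. Apply the reasonable-possibility sentence to the two uncovered rows.**

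- Consistent timing, other cause present: the sentence does not require other causes to be excluded, so the event can pass. It can be *associated* and still fail RELATED, which makes RELATED the stricter test.
- Timing ruled out, no other cause: no reasonable possibility remains, so the event fails this test too. The text does not assign it to NOT RELATED, but its ordinary meaning does. This row is a drafting gap only.

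**Step 3. Vary the simplifications.**

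- If a cause can be identified, only suspected, or absent, 2 of 6 combinations meet neither definition: consistent timing with an identified cause, and ruled-out timing with no cause. Consistent timing with a cause that is only suspected then counts as RELATED.
- If an indeterminate level of timing is added to the table in Step 1, 4 of 6 combinations meet neither.

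Consistent timing with an identified cause stays uncovered throughout.

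**Step 4. Trace where the label is used.**

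- *Tables.* Protocol 8.4 and SAP 8.6.1 tabulate treatment-related events. If all 28 subjects are dosed on a treatment, relabelling one subject moves a subject-incidence row by 1/28 = 3.6 percentage points, provided that the event is the subject's only related TEAE for that row and treatment. SAP 8.6.1 also counts TEAEs, and those counts can change as well.
- *Reporting after EOT or ET.* The follow-up call is 7 ± 2 days later, so the window is 7 − 2 = 5 to 7 + 2 = 9 days. A non-serious AE not labelled related in that window is not reported and cannot be recovered at analysis.
- *FDA-reportable status.* Appendix 1 requires an event to be both *associated* and *related*, so the stricter definition in effect limits the set. This conjunction does not tell the investigator which test to use for the two-way call.

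**The case against.** The strongest reply is that the definitions are called guidelines and leave the decision to the investigator. Every AE will still receive a label, and the reasonable-possibility sentence, placed directly under the two definitions, can naturally be read as the test that they serve. That reading is open, but no passage states it. Guidance that gives no answer for the mixed case leaves each investigator to supply one.

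The second reply is that little depends on the label, and much of this stands. All AEs from first dose to EOT or ET are recorded whatever their relationship and stay in the overall TEAE tables. SAP 8.6.6 plans no inferential safety analysis. The 24-hour SAE notification and the sponsor's SUSAR determination back up the FDA-reportable route, and Protocol 9.5 has the IRB informed of serious and unexpected AEs. Follow-up of related AEs that are still ongoing (Protocol 4.6 and 7.2.1) is optional. Healthy subjects, confinement and medication restrictions make competing causes less common.

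A reader might infer three stronger things that the documents do not support:

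- *That half of all combinations are unworkable.* Two of four cells are uncovered on paper, but only one would divide investigators.
- *That drug-related events will be under-counted, or that one lot is favoured.* The mixed event fails both definitions, so the text does not push it either way, and nothing ties the ambiguity to lot T or lot R.
- *That serious events could escape notice.* SAE notification does not depend on the label.

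**Conclusion.** The concern holds as a gap in definitions with limited reach. An AE with consistent timing and another identifiable cause meets neither category, while a looser test for a neighbouring term may be met, and precedence is unstated. Confidence is high on the wording; no such confidence attaches to any consequence.

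Three uses are exposed: the descriptive treatment-related TEAE tables, reporting of non-serious AEs during the 5 to 9 days after EOT or ET, and one of the conditions for FDA-reportable status, which has safeguards behind it. The number of affected events cannot be derived. The 3.6-point step is the size of one relabelled subject among 28, not an expected shift. The primary PK comparison does not use the label. This is a point to consider, not an obstacle to the trial.

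**What to change.** Reconcile the passages in Appendix 1 so that the two categories are complements under the standard the protocol already contains:

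- RELATED: there is a reasonable possibility that the drug caused the event.
- NOT RELATED: there is no reasonable possibility that it did.

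Keep time course and alternative causes as factors to weigh, not as joint conditions. *Associated* and *related* then mean the same thing in the definition of FDA-reportable AEs, and both uncovered rows are resolved.

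The cost is a short protocol amendment, with sponsor and investigator agreement (Protocol 9.1) and the IRB steps in Protocol 9.5. SAP 8.6.1 can stand, because it takes the investigator's label as given. The downside is that some more AEs may be labelled related, and a few more non-serious AEs may be reported after EOT or ET.
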